More frequent and longer assessment of moderators, mediators, and outcome(s) are necessary to elucidate the temporal dynamics between changes in specific mechanisms and treatment non-adherence behavior (Collins & Graham, 2002). Examining a broad array of factors impacting treatment non-adherence at multiple levels of analysis will enable a more comprehensive picture and will increase our ability to develop more impactful interventions for OUD.

Advances in **digital technologies and data analytics** have created new opportunities to assess and modify health behavior and thus accelerate the ability of science to understand and contribute to improved health behavior and health outcomes. Given the ubiquity of access to digital technologies worldwide, digital tools allow for the examination of health behavior and clinical trajectories within-individuals through intensive collection of individual-level, real-time data collected via surveys on mobile device (referred to as Ecological Momentary Assessment [EMA]), wearable sensors (on smartphones and/or smartwatches), and mapping digital footprints. Digitally-derived data allow for the development of dynamic models of health behavior to understand behavior in real-time and in response to changing environmental, social, physiological, and intrapersonal factors (Naslund et al., 2017; Spruijt-Metz, 2014). As applied to persons with OUD, digital data that offers ongoing assessment of behavior as individuals live their daily lives can help us better understand the trajectory of clinically important behaviors (e.g., treatment retention; medication adherence over time) and identify fluctuating contextual factors that greatly influence such behaviors, (e.g., patterns leading to relapse or treatment dropout).

Parent Study

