7.3 Other Outcome Measures

Other outcomes will include:

1. Frequency of missed buprenorphine doses based on EMA data;
2. Percentage of days with access to prescription medication exceeding a threshold (e.g., 80%) over the 12-week study period (a dichotomous variable based on pharmacy dispensation and medication orders from the EHR data extraction);
3. Number of days of non-prescribed opioid use (including illicit opioid use) in the last 4 weeks (weeks 9-12 post study consent) based on EMA data; and
4. Each non-prescribed opioid use event during the 12-week study period based on EMA data.
5. Each missed dose event during the 12-week study period based on EMA data.
6. Each missed visit to OUD treatment program during the 12-week study period based on EHR data.

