14.3 Statistical Methods for Primary and Secondary Outcomes

For our primary and secondary outcomes, we intend to use measures such as precision, recall (sensitivity) and specificity, F-score, to assess the quality of our predictions. The quality of the

identified digital phenotypes will be evaluated using cohesion (e.g., Silhouette score) and endpoint-differentiating power (e.g., Z-score).

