14.5 Types of Analyses

We are interested in measuring and predicting outcomes that may occur repeatedly over a 12-week observational period (e.g., patterns of daily drug use) using digital health technology. In digital health (Jain et al., 2015a) the spatio-temporal granularity of information about an individual is of higher resolution than that obtained through cross-sectional or traditional longitudinal studies. We will therefore assess the utility of using data from smartphones, smartwatches, social media and ecological momentary assessment to predict, explain and detect these outcomes.

Predicting outcomes using passively and actively collected digital health and social media data: Our approach to prediction will include regression-based methods (e.g., logistic regression), but we will also use common machine learning approaches for binary classification (e.g., random forest, support vector machines, K-means, gradient boosting). For each of these classification techniques, we will assess the utility of the various digital data for improving prediction quality. Typical evaluation methods used to assess the prediction quality include accuracy, precision, F-score, sensitivity (recall), and specificity. The relative utility of the various data for predicting outcomes will be assessed at two levels - individual features level and aggregated feature level. Interpretability of each feature and its contribution in predicting the outcome variable will be assessed using an ensemble framework, SHAP (Lundberg & Lee, 2017). In addition, we will also assess mutual information (Kraskov, Stogbauer, & Grassberger, 2004), which is a non-parametric approach of estimating the dependency between individual features and the target outcome. In another approach, features will be aggregated based on their gross categories (e.g., Facebook, Twitter, GPS, step, sleep, mood). The relative importance of each category will be evaluated based on its performance in predicting outcome (e.g., F-score).

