1. *Explaining temporal-causal relationships between factors determined to be useful for predicting outcomes:* Although machine learning methods may often be more effective for prediction than simple regression or correlation, they may be difficult to explain, or may not reveal insights regarding the relationships between factors. Therefore, we also include a set of analyses that are conducive to generating such explanatory or descriptive insights. For example, we will apply supervised metric learning and prototypical case-based reasoning (Hsueh et al., 2018), topic-modeling (e.g., Latent Dirichlet Allocation) and causal inference methods (Cheng, Bahadori, & Liu, 2014; Kleinberg & Hripcsak, 2011).
2. *Outcome detection using passively collected digital health data:* We plan to measure drug use and medication non-adherence events via EMA, multiple times a day. Since EMA requires a level of active engagement from participants that may not be realistic to expect outside of a research study, we plan to use machine learning to detect these events using only passively collected data. The methods used here would be similar to the machine learning methods previously described for binary classification.
3. *Feasibility of digital health technology:* We will generate descriptive statistical summaries of the level of adherence of study participants to the desired protocol (e.g., EMA response rate, smartwatch and smartphone wear/carry rate). No statistical inference is planned for this assessment.

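### For day- and event-level outcomes, 14.3 and 14.5 describe no per-person scoring, so the named measures can mix who has events with when they occur, and a feature with no timing information can rank first

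*Combined protocol and SAP*

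**What the plan says.** Section 14.5 aims to measure and predict "outcomes that may occur repeatedly over a 12-week observational period (e.g., patterns of daily drug use"). Section 7.3 lists outcomes at event level, including "Each non-prescribed opioid use event during the 12-week study period based on EMA data", each missed dose and each missed visit. Non-prescribed opioid use is also a secondary outcome in 7.2. For drug use and medication non-adherence, 14.5 item 2 adds detection: "we plan to use machine learning to detect these events using only passively collected data". It names no measure of its own and relies on methods similar to those for prediction.

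The measures are set out in two places. Section 14.3 intends "measures such as precision, recall (sensitivity) and specificity, F-score, to assess the quality of our predictions". Section 14.5 says "Typical evaluation methods used to assess the prediction quality include accuracy, precision, F-score, sensitivity (recall), and specificity". For groups of features, "The relative importance of each category will be evaluated based on its performance in predicting outcome (e.g., F-score"). For single features, "Interpretability of each feature and its contribution in predicting the outcome variable will be assessed using an ensemble framework, SHAP", with mutual information as a second approach.

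The synopsis (2.0) gives the rationale that "digital tools allow for the examination of health behavior and clinical trajectories within-individuals". Section 4.1.1 likewise points to differences within a person. Neither 14.3 nor 14.5 describes a score computed inside each participant, a benchmark that knows only a person's usual rate, or a split of features into personal average and daily deviation.

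**The concern.** Detecting an event is a question about timing: on which days did this person use, or miss a dose? A measure computed over all person-days also rewards a different ability, which is telling people who have many events from people who have few. A feature that is constant within a person, such as a habitual sleep level, says nothing about timing but can score well if it separates the two kinds of people.

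The study might then report that a passive signal detects drug use when it only marks higher-risk participants, or rank a stable trait above a signal that moves with the event. The secondary objective compares data sources with one another, and 2.4 intends the results to inform other studies. The temporal-causal step in 14.5 item 1 starts from factors already found useful for prediction, so a misleading ranking would carry into it. Holding out whole participants or clustering the standard errors does not help, because the issue is what the measure measures.

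**Working it through.** The plan gives no event rate, effect size or target score, so there is no stated figure to reproduce. From the documents come 50 to 75 participants (2.3) and 12 weeks, that is 12 × 7 = 84 days, or 4,200 to 6,300 person-days. All other inputs below are assumptions.

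**Exact example.** Suppose 10 of 50 participants use on 40% of their days and 40 never use.
- Person-days: 50 × 84 = 4,200. Event days: 10 × 84 × 0.40 = 336. Non-event days: 3,864.
- Rule A flags every day of the 10 users and knows nothing about timing. TP = 336, FP = 840 − 336 = 504. Precision = 336/840 = 0.40, recall = 1.00, F = 2 × 0.40 × 1.00/1.40 = 0.57. Specificity = 3,360/3,864 = 0.87. Accuracy = (336 + 3,360)/4,200 = 0.88.
- Rule B is a day-level detector with sensitivity and specificity 0.80 in everyone. TP = 268.8, FP = 0.20 × 3,864 = 772.8. Precision = 268.8/1,041.6 = 0.26, F = 0.39, accuracy = 0.80.

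Rule A is ahead on F, precision, recall, specificity and accuracy. Inside a user its sensitivity is 1 and its specificity 0, so sensitivity + specificity − 1 = 0. For rule B the same quantity is 0.60.

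**Simulation of the ranking.** Model: logit p(person i, day t) = μ + SD × b_i + log(OR) × x_it, with 84 days per person. The constant feature is a trait correlated 0.5 to 0.7 with b_i. The daily feature is x_it. Event days are 7% to 13% of all days. Each feature is scored by its best pooled F.

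| Person SD (logit) | Daily OR per SD | Studies in which the constant feature wins on F |
|---|---|---|
| 1 to 2 | 1.65 | 58% to 100% |
| 2 | 3 | 49% to 85% |
| 1 | 3 | 0% to 7% |
| 0.5 | 1.65 | 2% to 20% |

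**New people and mutual information.** A separate simulation (50 people, 60 replicates per scenario) set the cut-off in one cohort and scored it in different people. Its trait was stronger: b_i plus noise of SD 0.7, a correlation of 1/√(1 + 0.49) = 0.82. At 10% event days, SD 2 and OR 2, the constant feature had F 0.37 and mutual information 0.069, against 0.22 and 0.011 for the daily feature. It won in 92% of replicates on F and in 100% on mutual information. With no between-person variation (SD 0) it won on F in 0% to 3%. SHAP was not simulated.

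**Scored within person.** In that second simulation the mean within-person AUC of the constant feature was 0.50 in all 36 scenarios. For the daily feature it was about 0.61, 0.68 and 0.77 at OR 1.5, 2 and 3.

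**What within-person scoring loses.** Over SD 1 to 2 and 7% to 13% event days, about 2% to 32% of participants have no event day, and 24% to 69% have fewer than five.

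**The case against.** Five points can be made for the plan.

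- **Pooling is not stated.** The same measures could be computed within a person or averaged over people. This stands: the gap is that aggregation is unspecified. A reader might infer that the plan chose measures that reward who over when, but the text does not show such a choice.
- **The lists are open and not exhaustive.** Both metric sentences are worded as examples, and SHAP and mutual information are named too. This also stands. It helps little, since mutual information showed the same weakness.
- **Timing is addressed elsewhere.** Item 1 of 14.5 plans temporal-causal analyses. It names no score, however, and takes its factors from the prediction step.
- **Event detection is not the main question.** The primary objective is feasibility, the secondary objective concerns retention and adherence, and the study is an unpowered pilot. This limits the weight of the point. It does not remove it, because non-prescribed opioid use is a secondary outcome, detection is a planned analysis, and lack of power concerns precision and not what is measured.
- **Within-person figures are noisy and omit participants with no events.** This stands, and it is why they should sit beside the pooled figures and not replace them.

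**Conclusion.** The point holds for day- and event-level outcomes: non-prescribed opioid use, each missed dose, each missed visit, and the passive detection in 14.5 item 2. As described, the named measures do not separate who from when, so a feature with no timing information can rank first.

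A reader might go further and conclude that it will rank first. The documents do not support that. They give neither the between-person variation nor the strength of the daily signal. Under the assumptions above, the share of studies misranked runs from 0% to 100%: high when people differ a lot and the daily signal is weak, low when people differ modestly and the signal is strong or when they differ little.

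The point does not reach person-level outcomes (days retained, days covered, the 80% threshold), where knowing who is the aim. It is established for 14.3 and 14.5 only. Section 14.7 cites an Extended Data Analytic Plan for exploratory analysis, and that plan was not available. This is an inexpensive improvement to the plan and does not undermine its primary feasibility objective.

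**What to change.** In 14.3 and 14.5, for day- and event-level outcomes:

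1. State how each measure is aggregated over participants.
2. Beside the pooled measures, report within-person discrimination: the AUC inside each participant who has both event and non-event days, averaged over participants, with a participant-level bootstrap interval.
3. Split each time-varying feature into the person's mean over earlier days and the deviation from it, and report the two parts separately.
4. Show the ranking of data sources on both the pooled and the within-person measure.
5. Base any claim that a signal detects the timing of events on the within-person figure.
6. Report how many participants have no events and how many have few.

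The cost is SAP wording and modest extra analysis. The drawback is lower precision: participants without events drop out of the within-person figure, and many of the rest contribute few event days.

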This study is an ancillary study to CTN 0084 “Establishing an Opioid Registry Across Diverse Health Systems” (PI: [name]). An aim of CTN 0084 focuses on the use of EHR data from several health systems to examine the relationship between different lengths of buprenorphine retention and mortality. The optimal duration of buprenorphine treatment to reduce the risk of relapse, overdose, and mortality outcomes is unknown, although generally a longer length of treatment is related to better opioid use outcomes and lower risk of mortality (Dupouy et al., 2017; Sordo et al., 2017b; Weiss & Rao, 2017). However, retention in treatment remains a well-documented challenge and factors such as relapse, other substance use, inability to adhere to program stipulations, loss of insurance, cost, patient preference, provider practice, or health system policies can be related to discontinuation. CTN 0084 examines the distribution of buprenorphine retention, associated patient and health system characteristics, and rates of mortality, providing a high level view of this problem. This ancillary study complements the parent study by offering a “deep dive” into key factors associated with treatment retention (examining EHR data complemented by digitally-derived data) through data collected in real-time from a subset of patients in buprenorphine treatment for OUD as they live their daily lives. This ancillary study is a pilot, observational study and is not powered to test specific hypotheses.

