5.2 Secondary Objective(s)

The secondary objective is to examine the utility of EMA, digital sensing, and social media data (separately and compared to one another) in predicting OUD treatment retention, and buprenorphine medication adherence (as captured in EHR, medical claims, and EMA data).

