9.2 Site Characteristics

The AMRS programs at Kaiser Permanente Northern California (KPNC) offer a broad range of services (medical services onsite, group and individual therapy, family therapy). Staffing includes physicians, social workers, and substance use counselors. The AMRS programs offer MOUD treatment for buprenorphine.

We anticipate roughly 180 patients with OUD on buprenorphine for at least 2 weeks will be approached for recruitment. Assuming a conservative 30% recruitment rate, we anticipate approximately 50 (if recruitment is faster than anticipated, we will recruit up to 75) patients enrolled over the 6-month study recruitment period.

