14.2.2 Projected Number of Participants per Site

Approximately 50 (if recruitment is faster than anticipated, we will recruit up to 75) participants are projected to be recruited from KPNC.

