14.4 Significance Testing

The primary outcome will be evaluated using a two-sided test with a type I error rate of 5%. There are several secondary outcomes; however, multiple comparisons will not be adjusted for since these are not part of the study's primary objective as an observational study.

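### Section 14.5 compares data sources by predictive performance with no stated uncertainty for the difference; for outcomes that are one binary value per participant, equally useful sources will often differ by chance at 50 to 75 participants

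*Combined protocol and SAP*

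**What the plan says.** Section 5.2 sets out to "examine the utility of EMA, digital sensing, and social media data (separately and compared to one another"), with treatment retention and buprenorphine adherence as the targets of prediction.

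Section 14.5 does this at two levels. Individual features are assessed with SHAP and mutual information. Features are also grouped into categories, with six examples given (Facebook, Twitter, GPS, step, sleep, mood), and for these: "The relative importance of each category will be evaluated based on its performance in predicting outcome (e.g., F-score").

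Sections 14.3 and 14.5 list accuracy, precision, sensitivity, specificity and F-score. Neither attaches an interval, a resampling scheme or a paired comparison to any of them. Section 14.4 provides a 5% two-sided test for the primary outcome only and adds: "There are several secondary outcomes; however, multiple comparisons will not be adjusted for".

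On size, Section 14.2.2 states: "Approximately 50 (if recruitment is faster than anticipated, we will recruit up to 75) participants are projected to be recruited from KPNC". The synopsis adds: "This ancillary study is a pilot, observational study and is not powered to test specific hypotheses". Section 14.7 refers to an Extended Data Analytic Plan for exploratory analysis; that plan is not among the documents reviewed.

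**The concern.** A performance score computed on few participants with the event has a large sampling error, and so does the difference between two such scores. If only the scores are reported, a reader cannot tell a real difference between sources from noise.

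The point bears on outcomes that yield one binary value per participant. The 80% medication-access threshold in Section 7.3 is one. Retention and days covered in Section 7.2 are defined in days, but they would become binary if they were put through the binary classifiers that Section 14.5 names.

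Section 2.4 says the results should inform other HEAL studies and trials. An unqualified gap between sources could therefore influence which data streams later studies collect.

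**Working it through.** **The plan's own figures.** The documents state no power, precision, expected F-score or event rate, so there is no statistical figure to reproduce. The sample size is a recruitment projection: Section 9.2 expects about 180 patients to be approached, and 180 × 0.30 = 54, worded as approximately 50.

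**Inputs.** From the documents: 50 to 75 participants, 84 days (12 weeks), three sources (Section 5.2) and six example categories (Section 14.5). Assumed, because the documents give no value: event rate, true accuracy, and correlation between sources.

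**Step 1. One binary value per participant, all sources equal.** Each source gives a normal score with true AUC 0.70, that is, a mean shift of √2 × Φ⁻¹(0.70) = 0.74 SD in participants with the event. As many participants are flagged as have the event (e), so FP = FN = e − TP and

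F = 2TP / (2TP + FP + FN) = TP / e.

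Average best-minus-worst F-score gap (repeat runs agree to about 0.01):

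| Participants | Events | Correlation | Three sources | Six sources |
|---|---|---|---|---|
| 50 | 5 | 0.3 | 0.26 | 0.38 |
| 50 | 10 | 0.3 | 0.20 | 0.29 |
| 50 | 10 | 0.8 | 0.14 | 0.20 |
| 75 | 15 | 0.3 | 0.16 | 0.24 |
| 75 | 22 | 0.3 | 0.13 | 0.19 |
| 75 | 22 | 0.8 | 0.09 | 0.14 |

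The first and last rows are the extremes of the range examined (event rates of about 10 to 30%, correlation 0.3 to 0.8).

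**Step 2. A real difference.** With true AUCs of 0.75 and 0.65, correlation 0.3 and 20% events, the worse source has the strictly higher F-score in about 17% of studies at 50 participants and 14% at 75.

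**Step 3. A second model.** Six equal sources, sensitivity = specificity = 0.70 or 0.80, event rates of 20 to 50%, error correlation 0 to 0.8. The median best-minus-worst gap is 0.10 to 0.23 at 50 participants and 0.08 to 0.18 at 75. The chance of a gap of at least 0.10 is 45 to 97% and 23 to 93% respectively. For one pair, the 95% half-width is 1.96 × SD of the difference:

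- 50 participants: 1.96 × 0.056 = 0.11 to 1.96 × 0.131 = 0.26
- 75 participants: 1.96 × 0.045 = 0.09 to 1.96 × 0.107 = 0.21

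**Step 4. Repeated daily outcomes.** There are at most 50 × 84 = 4,200 to 75 × 84 = 6,300 person-days. With six equal sources, accuracy 0.75, daily event rates of 5 to 30%, outcome ICC 0.1 or 0.4, and between-person SD of logit accuracy 0 or 1, the median gap is 0.02 to 0.07. A gap of at least 0.10 occurs in 0 to 13% of studies, and of at least 0.05 in 0 to 80%. The higher values arise when accuracy varies between people.

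**Step 5. Would unadjusted intervals be enough?** Three sources make 3 pairs and six make 6 × 5 / 2 = 15. For equal sources, under a normal approximation with equal variances and correlations, the chance that at least one unadjusted 95% interval excludes zero is P(range > 1.96 × √2 × σ), where σ is the SD of a score's source-specific error. This is about 12% for three sources and 37% for six.

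**The case against.** The strongest reply is that this is a pilot that disclaims power, and that Section 14.5 opens with outcomes that recur daily. For those outcomes Step 4 shows that gaps of 0.10 or more are uncommon. This stands, and it limits the point mainly to participant-level outcomes. It does not remove it: retention is named in the secondary objective, and low power makes a statement of precision more useful.

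A reader might infer that Section 14.5 ranks the sources and keeps or drops them by score. The text does not say so. It says importance will be evaluated by performance, sets no ordering or discard rule, and uses SHAP and mutual information for individual features. Those two methods do not, however, quantify uncertainty in a difference between categories.

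The numerical assumptions are not anchored in the documents. Higher correlation between sources and higher event rates shrink the gaps: in Step 3, at 75 participants with a 50% event rate, accuracy 0.80 and correlation 0.8, a gap of at least 0.10 occurs in only 23% of studies.

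The Extended Data Analytic Plan may say more. It is cited for exploratory work only, whereas this is a secondary objective, but the omission can be asserted only for the documents available.

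**Conclusion.** The point holds in a limited form. The documents available specify no measure of uncertainty for the difference between data sources, although comparing them is a secondary objective. For outcomes analysed as one binary value per participant, equally useful sources will often differ by chance: on average by about 0.09 to 0.26 in F-score for three sources and 0.14 to 0.38 for six. This assumes event rates of 10 to 30%, a true AUC of 0.70 and correlation of 0.3 to 0.8.

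A reader might go further and infer that equal sources are bound to look clearly different on every outcome. The documents do not support that. They give no event rates, they define retention in days, and many of the planned outcomes are daily or event-level, where the median chance gap is about 0.02 to 0.07.

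Social media download is optional (Section 2.2), so comparisons involving it may rest on fewer than 50 to 75 participants.

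**What to change.** In Section 14.5, for each pair of sources, report the paired difference in performance on the same participants, with a 95% interval. Obtain the interval by resampling whole participants and repeating all fitting and tuning in each resample. Keep all copies of a resampled participant in the same fold, so that nobody is in both training and test data. Use the same participant-level resampling for daily outcomes.

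Present the intervals descriptively, and report a pair as not distinguished when its interval includes zero. State that one source is better only on simultaneous, multiplicity-adjusted intervals across the pairs, for the reason in Step 5.

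The cost is plan wording and computing time, with no added data collection or participant burden. The downside is less decisive statements: for participant-level outcomes at this size, many pairs are likely to be reported as not distinguished.
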